7.10.4.1 INTENSITY

The PI must grade the severity of all reported adverse events into one of five categories: Grade 1 (Mild), Grade 2 (Moderate), Grade 3 (Severe), Grade 4 (Life-Threatening) or Grade 5 (Death related to AE). The standardized CTCAE severity grading scales for the specific type of adverse event reported must be used when a matching CTCAE term is available. If no reference to a standard grading scale applies or is immediately available, use the following guideline:

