7.10.4.1.1 GRADE 1 –MILD

Persistence of any otherwise insignificant medical occurrence beyond 72 hours or any transient (< 72 hours) AE considered by the PI to be related to the study drug. No or minimal medical therapy or intervention required, hospitalization not necessary, no or little limitation in normal activities; nonprescription or single-use prescription therapy may be employed to relieve symptoms. Mild adverse events may be listed as expected consequences of the therapy for any given protocol, and standard supportive measures for such an expected event do not necessarily elevate the event to a higher grade.

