7.10.4.1.3 GRADE 3- SEVERE

Marked limitation in activity, some assistance usually required; medical intervention/therapy required; hospitalization possible or likely. [Specifically, for ocular adverse events in this vision related study, an immediately sight-threatening condition (e.g., impending corneal perforation, retinal detachment) may be categorized as Grade 3 if it would lead to total blindness in the affected eye(s).]

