8.3 ANALYSIS OF PRIMARY SAFETY ENDPOINTS

No formal inferential statistics will be performed on safety assessments. Statistical methods for the safety analyses will be primarily descriptive in nature. The Fludrocortisone acetate 1mg/0.1mL and 2mg/0.1 mL injection will be considered as safe and tolerable based on the number of subjects presenting severe AEs related to the study drug. It is understood that safety is a medical judgment that cannot be prospectively defined in detail. However, as general guidance, a subject will be considered to have tolerated a dose if the subject experiences no clinically significant drug-related adverse event or laboratory abnormality. Conversely, a subject will not be considered to have tolerated the dose if he experiences a clinically significant drug-related adverse event or laboratory abnormality during the study drug administration or post-administration follow-up period.

Listings and summaries for all safety data will be presented using the Safety Population. Descriptive statistics (mean, SD, median, minimum and maximum) will be calculated for summaries of continuous safety data and frequency counts and percentages (where appropriate) will be calculated for summaries of discrete/categorical safety data.

Adverse events (AEs) will be coded using the Medical Dictionary for Regulatory Activities (MedDRA), and data will be summarised by System, Organ, Class and preferred term. The number and percent of participants reporting each AE will be summarised descriptively (n=9). A participant with two or more AEs within the same level of summarisation (i.e., system, organ, class or preferred term) will be counted only once in that level. The number of AEs reported will also be presented. Adverse events will also be summarised by severity as well as relationship to study treatment. A by-participant AE data listing, including verbatim term, preferred term, system organ class, severity, and relationship to study treatment, will be provided. Separate listings will be generated for SAEs and AEs leading to study/treatment discontinuation.

All haematology, blood chemistry and urinalysis (continuous variables) parameters will be summarised using descriptive statistics for all study visits assessed, including change from baseline (last pre-surgery value) for all post-surgery assessments. All laboratory data will be included in the data listings and all test values outside the normal range will be flagged.

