8.6 SAMPLE SIZE

The study is planned to enrol up to 12 participants with geographic atrophy secondary to age-related macular degeneration with visual acuity (20/32 to 20/2000, Snellen's equivalent), following the 3+3 method.

The sample size chosen for this study was selected without formal statistical justification, but the numbers chosen are considered adequate for assessing the study objectives. The sample size was determined on the basis of practical and logistical considerations and not based on statistical power with regard to hypothesis testing or precision with regard to parameter estimation.

This phase 1 trial was designed to identify any important limiting toxicities and to determine if this dose is suitable for phase 2 trial. This was also designed to minimize the likelihood that a minimum number of subjects will be exposed to the investigational drug.

This is an open label study, and no randomization is conducted in this study.

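### The safe-and-tolerable conclusion in section 8.3 rests on severe drug-related AEs and uses neither the DLT count nor the count of subjects who did not tolerate the dose

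*Protocol*

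**What the plan says.** Protocol section 8.3 states that the 1 mg and 2 mg injections "will be considered as safe and tolerable based on the number of subjects presenting severe AEs related to the study drug". No number is attached. The paragraph continues: "It is understood that safety is a medical judgment that cannot be prospectively defined in detail". It then offers, as general guidance for the individual, that "a subject will be considered to have tolerated a dose if the subject experiences no clinically significant drug-related adverse event or laboratory abnormality". The same guidance stands in section 6.2.

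The DLT is defined in the synopsis and section 6.2 as any of four event types within 28 days of injection: intraocular inflammation, raised IOP, a loss of at least 15 letters, or haemorrhage. No severity grade is attached. It governs escalation (5.2.1, 6.2) and stopping of enrolment (synopsis, 6.2). Section 8.6 describes the trial as "designed to identify any important limiting toxicities and to determine if this dose is suitable for phase 2 trial". Section 8.3 does not mention it.

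On grading, section 7.10.4.1 puts CTCAE first: "The standardized CTCAE severity grading scales for the specific type of adverse event reported must be used when a matching CTCAE term is available". Only otherwise does a fallback apply: "If no reference to a standard grading scale applies or is immediately available, use the following guideline". In that fallback, Grade 1 (7.10.4.1.1) covers otherwise insignificant events that last beyond 72 hours, or "any transient (< 72 hours) AE considered by the PI to be related to the study drug". Grade 3 (7.10.4.1.3) has a general criterion of marked limitation with intervention required, plus a bracketed ocular clause that refers to total blindness of the affected eye.

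**The concern.** The outcome that the trial is built to detect does not enter the sentence that states how its doses will be judged. Three tests of harm stand side by side (severe related AE, DLT, not tolerated), and only the first is named as the basis for the dose-level conclusion. They are not nested: a DLT needs no grade, and failing the tolerability test needs no grade either.

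At stake is the closing statement on safety, which feeds the decision on Phase 2. That statement could be silent on toxicities recorded in the same participants.

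The second issue is smaller. Severity is half of the primary endpoint (number and severity of treatment-emergent events), and 8.3 summarises severity and relationship to treatment as separate attributes. For events graded on the fallback scale, the two are partly the same judgement.

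**Working it through.** The protocol gives no DLT rate, severe-AE cut-off or operating characteristic, so there is no planned figure to reproduce. The check is first textual, then illustrative.

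**The three tests for one subject**

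| Test | Where | Needs a severity grade? | Needs relatedness? | Named as basis for the dose conclusion in 8.3? |
|---|---|---|---|---|
| Severe related AE | 8.3 | Yes | Yes | Yes |
| DLT | Synopsis, 6.2 | No | Not in the definition; yes in the 6.2 stopping rule | No |
| Not tolerated | 6.2, 8.3 | No (clinical significance) | Yes | No, per subject only |

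Example: a drug-related fall from 70 to 54 letters on Day 14. The loss is 70 − 54 = 16 letters, and 16 ≥ 15, so it is a DLT. If judged clinically significant, the subject has not tolerated the dose. Whether it counts under the 8.3 basis depends on its grade, which the documents do not settle.

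Two further provisions can separate the counts. A DLT judged unrelated drops out of the 8.3 count. Section 7.11.3 keeps unequivocal AMD progression, including lesion bleeding, from being recorded as an AE in the CRF, although haemorrhage is a DLT component.

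**How often the counts could diverge**

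Input from the synopsis: n = 6 at 2 mg. My assumptions, not document figures: DLT rate p; share s of DLTs graded severe; subjects independent; all six dosed; all DLTs related; severe AEs arise only among DLTs.

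P(≥3 DLTs and 0 severe) = Σ over x = 3 to 6 of C(6,x) · p^x · (1−p)^(6−x) · (1−s)^x

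| p | s = 0 | s = 0.25 | s = 0.5 | s = 1 |
|---|---|---|---|---|
| 0.3 | 0.256 | 0.100 | 0.027 | 0 |
| 0.5 | 0.656 | 0.231 | 0.057 | 0 |
| 0.7 | 0.930 | 0.273 | 0.055 | 0 |

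For p = 0.5 and s = 0.25 the terms are 0.1318 + 0.0742 + 0.0222 + 0.0028 = 0.231. Divergence is possible whenever s < 1. Its size is driven by s, which the protocol does not fix.

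**What a zero severe count would show**

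The one-sided 95% upper bound on the severe-AE rate after zero events is 1 − 0.05^(1/n): 63% for n = 3, 39% for n = 6, 28% for n = 9. An absence of severe AEs says little by itself.

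**Denominator**

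Section 8.3 gives AE percentages on n = 9. Three affected subjects at 2 mg would be 3/6 = 50% by dose but 3/9 = 33% pooled.

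**The case against.** A reader might infer more than the text supports, in three ways.

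- **That 8.3 would call a dose safe even if all six subjects at 2 mg had a DLT.** It does not say so. It sets no count, defers to medical judgement, and its own guidance would class subjects with clinically significant related events as not tolerating the dose. Enrolment also stops when more than two patients have a DLT, a sentinel subject is followed for 28 days before the other five are recruited, and the DSMB criteria in 9.7 include a 15-letter loss, an IOP change and inflammation.
- **That a related event under 72 hours is Grade 1 whatever its peak.** The fallback Grade 1 also requires little or no treatment and little or no limitation of activity, and the fallback applies only when CTCAE does not.
- **That total blindness is the only ocular route to Grade 3.** The clause is permissive and adds to a general criterion that is not restricted to non-ocular events.

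It can also be said that DLT data are not hidden. Section 8.3 requires AE listings by participant, 8.4 summarises BCVA and IOP change, and a DLT table is routine SAP content.

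These points remove the strong reading but leave the narrow one. The stop governs enrolment, not the conclusion, and no stagger is stated for the last five subjects at 2 mg. Sections 5.2.1 (no DLT in three) and 6.2 (no more than two) also differ on escalation. The tolerability guidance stays at subject level. Listings do not alter the criterion, and that criterion is fixed in the protocol rather than left to the SAP.

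**Conclusion.** The point holds in this form: the stated basis for calling the doses safe and tolerable bypasses both the trial's own toxicity outcome and the stricter tolerability test in the same paragraph. A dose with several DLTs or non-tolerating subjects could show few or no severe related AEs, and the criterion as written would not register them.

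The size cannot be fixed from the documents, because they do not give CTCAE grades for the DLT event types. Under the assumptions above, the probability for six subjects runs from 0 (all DLTs graded severe) to 0.930 (p = 0.7, none graded severe). The claim is that the conclusion and the DLT record can diverge, not that 8.3 would declare a plainly toxic dose safe.

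The Grade 1 wording is a secondary defect, confined to events with no applicable CTCAE scale.

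**What to change.** 1. In 8.3, state that the dose-level conclusion rests on, and reports separately by dose (planned n = 3 at 1 mg and n = 6 at 2 mg), the number of subjects with a DLT and the number not tolerating the dose, beside the number with related Grade 3 or higher AEs. Medical judgement can still be applied to these counts. The denominators follow the synopsis and 6.2; the total of up to 12 in 8.6 has to be reconciled with them.
2. In 7.10.4.1.1, remove the relationship-to-drug and 72-hour wording, so that severity is graded on intensity alone and causality is recorded only under 7.10.4.2.
3. Ask the sponsor to reconcile the ocular Grade 3 clause in 7.10.4.1.3 with the DLT definition in 6.2. This review does not propose a threshold.

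The cost is protocol and CRF-guideline wording and one additional summary table. No new data, visits or subjects are needed. The downside is that some events may be graded higher and the safety summary may look less favourable. Because the DLT components for IOP and inflammation carry no threshold, minor events could also enter the DLT count, which is a reason to show the three counts together.

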8.4 ANALYSIS OF SECONDARY ENDPOINTS

The efficacy endpoints are the secondary endpoints of this study, which include complete ocular examination.

ETDRS best-corrected visual acuity (BCVA) will be scored with reference to the Early Treatment Diabetic Retinopathy Study ETDRS letters). ETDRS will be treated as continuous data, and descriptive statistics (mean, SD, median, minimum and maximum) will be summarised for ETDRS observed value and change from baseline at each post-

surgery visit. Exploratory analysis of ETDRS change over time will be assessed by using a mixed model. The correlations between repeated measures of the same participant will be accounted for by the mixed model. The least squares mean of ETDRS change from baseline and its 95% confidence interval at each visit will be estimated. Similar analyses will be conducted for intraocular pressures. Categorical efficacy endpoints such as slit lamp biomicroscopy exam findings, dilated ophthalmoscopy exam findings, color fundus photography and OCT finding will be summarised descriptively by frequency count and percentage (proportion) where appropriate.

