2.3.3 RISK/BENEFIT

The safety monitoring practices employed by this protocol (e.g. complete ophthalmologic exam, IOP monitoring, OCT, vital signs, hematology, serum chemistry, and AE questioning) are adequate to protect the subjects' safety.

There are risks associated with the ophthalmic procedures required for participants in this study. However, these are all standard procedures that are widely performed in ophthalmology.

In the days following any IVT injection, patients are at risk of developing endophthalmitis. If the eye should become red, sensitive to light, painful, or develop a change in vision, the patient will be instructed to seek immediate care from an ophthalmologist. Other risks of IVT injection include traumatic cataract, retinal detachment and hemorrhage.

Transient increased IOP has also been identified as a risk following IVT injections. IOP will be carefully monitored in this study.

The approximately 150 mL of blood (See Section 9.9) planned for collection from each subject over the 6 months of the study does not pose an undue risk in this patient population.

Based on data available to date, IVT administration of Fludrocortisone acetate does not seem to present an unreasonable ophthalmic or systemic risk in animal models. Fludrocortisone acetate has been safely used systemically as mineralocorticoid replacement for severe orthostatic hypotension in Addison's disease and other salt-water imbalances.

However, as Fludrocortisone acetate has not been used intravitreally in human participants there are potential unforeseen risks. To mitigate such risks, this study is being conducted in two parts, restricting treatment to a single individual together with extended assessment, prior to application in other participants. Numerous follow-up visits and numbers of testing procedures have also been instituted in the assessment schedule for all participants to ensure adverse events, or other safety issues that arise are identified and addressed in a timely manner.

There is a potential health benefit for trial participants from receipt of study drug. We propose to administer intravitreal Fludrocortisone acetate to patients with GA. If efficacious, intravitreal Fludrocortisone acetate is expected to alter the course of GA and slow its rate of progression.

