3.2.2 SECONDARY ENDPOINTS

- The change in square root geographic atrophy (GA) lesion size from baseline to Month 6 as measured by FAF.
- Change in best corrected visual acuity (BCVA).
- Change in low luminance best corrected visual acuity (LL-BCVA).
- Relationship between GA lesion size changes and changes in BCVA.
- Change in vital signs.

- Increase in intraocular pressure (IOP).

Pharmacokinetic (PK) parameters

- Exposure after single dose Fludrocortisone acetate IVT injections.
- Serum maximum observed concentration.
- Time to maximum measured concentration
- Terminal elimination half-life.

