8.1 POPULATION FOR ANALYSIS

- Safety Analysis:

All subjects who received at least one dose of treatment will be included in the evaluation of safety of FCA.

- Efficacy Endpoint(s):

The efficacy analysis will be based on an intention-to-treat population (ITT), which is defined as all subjects who received the single dose of treatment and have at least one visit at or after month 2. Month 2 is the first visit on treatment at which lesion area is measured. Per protocol (PP) efficacy analyses will include all randomized subjects who return for Day 150 of follow up.

Safety is the main analysis population for safety endpoints, and ITT is the main analysis population for efficacy endpoints. The assignment of participants to each analysis population will be based on the review of data after the completion of all data collection, monitoring by the clinical research associate and first round of query resolution by data management and prior to database lock.

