8.2 DEMOGRAPHIC AND BASELINE CHARACTERISTICS

Participant demographic and baseline variables (age, sex, ethnicity, race, height, weight, and BMI) will be summarised with descriptive statistics. Sex, ethnicity, and race will be summarised with frequency counts and percentages. Baseline ocular assessments will be summarised descriptively as well.

Pregnancy test results, concomitant medication and medical history data for each participant will be presented in data listings. Concomitant medications will be summarised descriptively by using frequency counts and percentages.

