9.7 DATA SAFETY MONITORING BOARD

An independent DSMB will be convened. The mission of the DSMB will be to ensure the ethical conduct of the trial and to protect the safety interests of patients in this study. The DSMB will be responsible for reviewing the cumulative safety results from the study. The DSMB will meet prior to the commencement of the study, and will review all

available safety/tolerability data (e.g., adverse events, serious adverse events, clinical laboratory assessments, blood pressure, haematology, urology) at Day 0 and 1 month after IVT injection of FCA of the initial participant in Part 1 and 3 (prior to Part 2 & 4 of the study), and convene as required throughout the study period to review data and potential safety risks. The criteria for evaluating study continuation will relate to study safety, including the incidence and severity of ocular and/or systemic side effects not limited to but including; change in IOP of >10mmHg, a loss of 15 letters or more in BCVA, presence or intraocular inflammation, presence or absence of ocular pain, change in BP of 30mmHg (systolic or diastolic), incidence of hospitalisation or systemic illness, and any other ocular or systemic adverse events reported. Any changes will be referenced to baseline measurements. The DSMB will then meet at the conclusion of the study and after the final statistical analysis in order to review all data.

DSMB will consist an ophthalmologist, and a biostatistician, both independent of the study team.

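### IOP is summarised only visit by visit and as an efficacy endpoint; present it in the Safety Population and add a count by dose of participants with a measured rise

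*Protocol*

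**What the plan says.** **Endpoint and analysis.** Section 3.2.2 and the synopsis list an increase in IOP among the secondary endpoints. Section 8.4 opens with "The efficacy endpoints are the secondary endpoints of this study, which include complete ocular examination". It then describes the BCVA analysis: mean, SD, median, minimum and maximum of the value and of its change from baseline at each visit, plus an exploratory mixed model giving a least squares mean change with a 95% interval at each visit. For IOP it adds only "Similar analyses will be conducted for intraocular pressures". The synopsis says the same under Efficacy Analysis. The examples in 8.4 of items to be summarised by count and percentage (slit lamp, ophthalmoscopy, fundus photography, OCT) do not include IOP.

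**Population.** Section 8.1 bases efficacy on an ITT population, "which is defined as all subjects who received the single dose of treatment and have at least one visit at or after month 2". The synopsis defines ITT more loosely: treated participants with at least one efficacy measurement after dosing. The safety data named in the synopsis and in 8.3 are adverse events, laboratory tests, vital signs and physical examinations. IOP is not named.

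**Where IOP appears for individual participants.**
- Elevated IOP within 28 days is a dose-limiting toxicity, with no number attached (synopsis, 6.2).
- Two IOP events are of special interest: 30 mmHg sustained at or past 90 minutes after injection, and any rise needing surgical intervention (7.10.3).
- Section 8.3 plans adverse-event counts and listings. For treatments, section 8.2 says "Concomitant medications will be summarised descriptively by using frequency counts and percentages".
- The safety board's criteria in 9.7 include "change in IOP of >10mmHg, a loss of 15 letters or more in BCVA", measured from baseline.

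**The concern.** The introduction (2.2) names ocular hypertension as a complication of intravitreal corticosteroids, and 6.2 follows the first participant for 28 days to look for an IOP response. The study is meant to support Phase II (3.1). The figure a Phase II team would want is how many treated participants at each dose had a raised IOP. A by-visit summary describes each visit's readings without linking them across visits, so it does not contain that figure. Handling IOP as efficacy also ties it to a population whose month-2 condition is explained in 8.1 by when lesion area is measured. That reason has no bearing on IOP, which is measured from Day 1.

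**Working it through.** The protocol gives no IOP response rate, threshold for this endpoint or precision figure, so there is no stated result to reproduce.

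**Inputs.** Cohorts of 3 (1 mg) and 6 (2 mg), from the synopsis. Seven post-dose IOP visits (Days 1, 7, 14, 28, 60, 90, 150), from section 1.2. A value of >10 mmHg change from baseline, from 9.7. *Assumed:* a raised reading is +15 mmHg (14 to 29) and all other changes are 0.

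**1. Same tables, different counts.** In case A, one participant is raised at Days 28 and 60. In case B, one is raised at Day 28 and another at Day 60. At each of the two visits, in both cases:

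| Cohort | Mean change | SD | Median | Max | Count >10, A | Count >10, B |
|---|---|---|---|---|---|---|
| 6 | 15/6 = 2.5 | 15/√6 = 6.12 | 0 | 15 | 1/6 (17%) | 2/6 (33%) |
| 3 | 15/3 = 5.0 | 15/√3 = 8.66 | 0 | 15 | 1/3 (33%) | 2/3 (67%) |

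Exchanging two participants' changes at one visit leaves every by-visit statistic of change as it was. With complete data and visit as the only fixed effect, the least squares means are the visit means, so they do not move either. A baseline covariate might shift them slightly but would still give no count.

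**2. How wide the ambiguity can be.** Take changes of {12, 3, 2, 1, 0, −1} at every one of the 7 visits. Each visit then shows mean 17/6 = 2.83, SD 4.71, median 1.5 and maximum 12. This fits 1 of 6 participants above 10 mmHg (always the same person) or 6 of 6 (the high value moving between people). With {12, 1, 0} it fits 1 of 3 or 3 of 3.

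**3. Population.** Suppose one participant is at +15 on Day 28 and leaves before month 2, with the others at 0. Under 8.1 that person is out: the Day 28 mean change becomes 0 instead of 2.5 in the cohort of 6 (5.0 in the cohort of 3), and a count in that population would be 0/5 instead of 1/6 (0/2 instead of 1/3). Under the synopsis definition the person stays in.

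**4. Treatment.** If a +15 at Day 28 is treated down to between 0 and +3, the later mean change is 0 to 3/6 = 0.5 (0 to 3/3 = 1.0), against 2.5 (5.0) untreated. The Day 28 maximum still shows +15.

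**5. What the added count can bear.** Exact 95% intervals (Clopper-Pearson; lower limit the 2.5% point of Beta(x, n−x+1), upper limit the 97.5% point of Beta(x+1, n−x)): 1/3, 0.8% to 91%; 2/3, 9% to 99%; 1/6, 0.4% to 64%; 2/6, 4% to 78%.

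**6. False positives.** *Assume* normal noise, no true change, 7 visits sharing one baseline reading, and a change SD of 2, 3 or 4 mmHg. Let s = SD/√2. The chance per participant of any change >10 mmHg is p = 1 − ∫ φ(b; 0, s) Φ((10+b)/s)⁷ db, which is under 0.001%, 0.27% and 3.4%. For at least one of 9 participants, 1 − (1 − p)⁹ gives under 0.1%, about 2.4% and about 27%.

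**The case against.** **A threshold table is normally left to the statistical analysis plan, and 8.4 excludes nothing.** This carries some weight, and it keeps the point small. But the protocol does state an IOP analysis and places it under efficacy with its own population. That choice suits a known steroid risk poorly, so it is fair to correct it here.

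**An increase in IOP can be read as mean change, and the maximum exposes a large rise.** Both are true. The maximum shows that someone was high at that visit, but not how many people were high over the study.

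**Participant-level coverage already exists.** This is largely right. Dose-limiting toxicity is judged per patient and dose level (5.2.1), the events of special interest are reported individually, and 8.3 promises listings of safety data, so with 9 people a hand count may be possible. None of these is a planned count of measured rises. The toxicity criterion has no number and stops at 28 days. A rise from 14 to 29 mmHg does not reach the 30 mmHg criterion. Adverse-event counts depend on the investigator reporting the rise as an event.

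**Stronger readings that the documents do not support.**
- A reader might infer from the n=9 in 8.3 that adverse events will not be split by dose. It is a denominator and does not bar dose columns; the same section speaks of both dose strengths when judging safety.
- A reader might infer that an early leaver is certainly lost from the IOP summary. That follows from 8.1 but not from the synopsis; the two definitions differ.
- A reader might take >10 mmHg as the protocol's definition of raised IOP. In 9.7 it is one item in an open-ended list for board review, worded as a change. It is a convenient existing value and no more.

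**Conclusion.** The point holds as a minor one. The IOP analysis in 8.4 and the synopsis is by visit only, and such summaries do not determine how many participants at each dose had a rise. The same tables can fit 1/6 or 2/6 in a simple example, and 1/6 or 6/6 at the extreme. The population is at best unclear, because 8.1 and the synopsis differ on an early leaver. The non-identifiability is exact and needs no assumption. The example sizes rest on assumed rises of 12 or 15 mmHg, and the false-positive figures on an assumed SD. A reader might infer that a raised IOP would go unnoticed, or that escalation rests on this summary. Neither follows: toxicity review, special-interest reporting and the safety board work from individual data. With cohorts of 3 and 6 the added count is descriptive only.

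**What to change.** In 8.4 and the synopsis:

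1. Keep the by-visit statistics and the mixed model for IOP, but present IOP in the Safety Population.
2. Add a descriptive count by dose (x/3 and x/6 as planned) of participants whose study-eye IOP rose by more than 10 mmHg from the last pre-injection reading at any scheduled or unscheduled post-dose visit.
3. Show the Day 0 post-injection check (7.8) on its own line, since 2.3.3 notes "Transient increased IOP has also been identified as a risk following IVT injections".
4. Beside the count, as separate lines and not merged into a composite, give the number with IOP above 30 mmHg (the value in 7.8) and the number starting IOP-lowering treatment, leaving out the routine pre-injection decompression in 5.2.3.

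The cost is wording and a few table lines. IOP is already scheduled at every visit (1.2), unscheduled assessments go into the eCRF (6.3.6), and concomitant treatment is recorded with dates and indication (5.3). The downside is slightly more reporting and an occasional false positive from measurement noise. Sample size, escalation and tolerability decisions stay as they are.
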